**All women in this study will be subjected to the following:**

**I. History:**

- a. Personal** (age, duration of marriage, educational level, special habits).
- b. Menstrual:** LMP to detect Gestational age expressed in weeks which calculated from first day of LMP. For patients who underwent in vitro fertilization, gestational age will be calculated from the date of the embryo transfer.
- c. Obstetric history:** all patients will be primigravida.
- d. Past history:** of any medical disease or surgical operation.
- e. Family history:** of any hereditary or non-hereditary disease.
- c. Present history:** of any symptoms during pregnancy, analysis of any complain, investigations will be done and treatment will be given during pregnancy.

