#### **A. Inclusion criteria:**

- Primigravida Women with singleton pregnancies aged 20 to 34 years in control group and aged 35 y or more in case group, natural conception or with using ART, who seeking for routine antenatal care to the university hospital and who will accept the study protocol.

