## Sample size

Sample size was calculated by PASS 15 Power Analysis and Sample Size Software (2017). NCSS, LLC. Kaysville, Utah, USA, [ncss.com/software/pass](http://ncss.com/software/pass).

Based on previous studies including Yogev et al. (2010), the authors hypothesize an overall poor outcome in 20% of young pregnant group vs. 60% in elderly pregnant group with a prevalence of elderly pregnant ladies of 25% vs. 75% of young pregnant ladies.

A logistic regression of a binary response variable (Y) on a binary independent variable (X) with a sample size (N) of 80 observations (of which 50% are in the group X=0 [40 young pregnant ladies] and 50% are in the group X=1 [40 elderly pregnant ladies]) achieves 94% power at a 0.050 significance level to detect a change in Prob (Y=1) from the baseline value of 0.200 to 0.600. This change corresponds to an odds ratio of 6.000. A two-sided Wald test is used.

Considering a possible dropout rate (DR) of 20%, the expected number of dropouts will be 20, and the dropout-inflated enrollment sample size (N') will be 100 participants (50 young, and 50 elderly) where  $N' = N / (1 - DR)$ .

- We will have 2 groups: the **first** group will be represented by 50 women aged 35 y or more and the **second** group will be represented by 50 women aged from 20 to 34 y.
- **The first group** will be also divided into 2 subgroups: group (1A) aged from 35y to 40 y, the group (1B) aged above 40 y and we will compare between the outcomes in the 2 groups which include maternal, obstetric, fetal and perinatal outcomes.
- We will also compare between those with spontaneous pregnancy and those with ART.

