### **III. Investigations:**

- All pregnant women will undergo routine investigations at the first antenatal visit which include: CBC, RH grouping, blood grouping, urine analysis, fasting and postprandial blood glucose.

-All pregnant women will be screened for gestational diabetes mellitus (GDM) with a 50-g oral glucose challenge test between 24 and 28 weeks of gestation. Women with abnormal glucose challenge test (140 mg/dL) will undergo a 3-hour oral glucose tolerance test with a 100-g oral glucose load. The diagnosis of GDM will be made when levels of blood glucose are fasting plasma glucose above 95 mg/dL, 1 hour postprandial above 130-140 mg/dL, and 2 hours postprandial above 120mg/dL according to The American College of Obstetricians and Gynecologists (ACOG) recommendations (17).

- All pregnant women will undergo a monthly ultrasound examination until delivery.

- All obstetrical and clinical data will be recorded and collected in an appropriate database.

-Obstetric outcomes will be recorded regarding pregnancy induced hypertension, gestational diabetes mellitus (GDM), anemia, antepartum hemorrhage, oligohydraminos or polyhydraminos, obtetretic shock and intrapartum hemorrhage.

-Maternal outcomes will be recorded regarding mode of delivery “cesarean or vaginal delivery”, premature rupture of membranes, preterm birth which is defined as delivery of an infant before 37 weeks of gestation and will be classified into late preterm (from 34 to less than 37 weeks of gestation) and early preterm birth (delivery from 28 to 34 weeks of gestation), obstructed labor and prolonged labor.

-Fetal outcomes will be recorded regarding congenital malformations, intrauterine growth restriction, intrauterine fetal death and stillbirth.

- Perinatal outcomes will be recorded regarding birth weight which will be classified into low birth weight (less than 2500 g), very low birth weight (less than 1500 g) and macrosomia (more than 4000 g), birth asphyxia, meconium aspiration syndrome, NICU admission, neonatal hypoglycemia, Hyperbilirubinemia, 5-Min Apgar score less than 7 and neonatal death.

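### Non-IVF pregnancies are dated by LMP with no rule for using the planned scans, so preterm birth can be misclassified and group contrasts diluted

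*Combined protocol and SAP*

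**What the plan says.** Under "I. History", item b (Menstrual), the default is "Gestational age expressed in weeks which calculated from first day of LMP". The single exception follows: "For patients who underwent in vitro fertilization, gestational age will be calculated from the date of the embryo transfer". No conversion from transfer date to menstrual weeks is given.

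Under "III. Investigations" the protocol states: "All pregnant women will undergo a monthly ultrasound examination until delivery". It does not say how early the first scan is, or that any scan confirms or corrects the LMP date. Nor does it say what happens when the LMP is uncertain.

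The same section records "preterm birth which is defined as delivery of an infant before 37 weeks of gestation", with a further split at 34 weeks. Growth restriction appears only in a list ("congenital malformations, intrauterine growth restriction, intrauterine fetal death and stillbirth"), without a definition, percentile or reference chart.

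The inclusion criteria admit "natural conception or with using ART", and the "Sample size" section adds: "We will also compare between those with spontaneous pregnancy and those with ART".

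**The concern.** Preterm birth and its two classes are thresholds on gestational age, so an error of a few days in dating moves women near 37 weeks across the line in either direction. LMP dates are open to recall and cycle-length error. The plan names LMP as the method and schedules scans that could check it, but does not connect the two. Followed as written, it can give a poorer classification than its own procedures would allow.

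Two comparisons are at stake. In the age comparison, similar error in both groups dilutes the preterm contrast. The spontaneous-versus-ART comparison also sets two dating methods against each other, so part of any difference in preterm birth could come from measurement.

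**Working it through.** **1. The plan's own figure.** For 40 per group and 0.20 versus 0.60, the Wald power is Φ(ln 6 / √(1/(40·0.2·0.8) + 1/(40·0.6·0.4)) − 1.96) = Φ(1.792/0.510 − 1.96) = 0.940. The enrolment figure is 80/(1 − 0.20) = 100. Both match the "Sample size" section. This point concerns measurement and does not alter them.

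**2. Inputs.** From the protocol: the 37-week cut, 259 days. Everything else is assumed, because the documents give no dating error:
- true preterm rate 10% (comparator 25%);
- term births Normal(277, SD 8) days, restricted to 259 days or more;
- LMP error with mean +1 or +2 days and SD 5 or 7 days, with 0% or 10% of women having a large error (SD 21 days), giving eight settings;
- three shapes for true preterm gestation: exponential below 259 days with mean 14 or 21 days, or uniform on 196–259 days.

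**3. Formulas.** Se is the share of true preterm births dated below 259 days. Sp is the share of term births dated at or above 259 days.
- Missed = 1 − Se
- Observed rate = p·Se + (1 − p)(1 − Sp)
- False share = (1 − p)(1 − Sp) / observed rate
- Observed contrast = (0.25 − 0.10)(Se + Sp − 1)

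**4. Results** (3 million births in each class per setting; ranges over the eight error settings):

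| Preterm shape | Missed | False share at 10% | Observed at true 10% | Observed at true 25% | Contrast (true 15) |
|---|---|---|---|---|---|
| Exponential, mean 14 | 14.5–21.7% | 10–34% | 9.2–12.3% | 21.4–23.8% | 11.2–12.6 |
| Exponential, mean 21 | 10.4–16.1% | 10–33% | 9.7–12.8% | 22.6–25.0% | 12.0–13.2 |
| Uniform 196–259 | 4.0–7.1% | 9–31% | 10.4–13.6% | 24.5–26.9% | 13.3–14.2 |

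One setting worked through (exponential mean 14, error +2 days, SD 7, 10% large): Se = 0.783 and 1 − Sp = 0.0397. The observed rate is 0.0783 + 0.9 × 0.0397 = 0.114, the false share is 0.0357/0.114 = 31%, and the contrast is 15 × (0.783 + 0.9603 − 1) = 11.2 points. Seven of the eight error settings give a false share of 9–31% and an observed rate of 9.2–12.8%. The eighth (+1 day, SD 7, 10% large) reaches 34% and 13.6%.

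**5. A different model.** With all gestations Normal(275, SD 13), the true preterm rate is 10.9%. Unbiased error of SD 3, 5 and 7 days gives observed rates of 11.5%, 12.5% and 13.9%, with Se 0.87, 0.81 and 0.76. A bias of +2 to +3 days with SD 5–7 gives 9.8–11.1%, with Se 0.63–0.71. For a second group at Normal(272, SD 15), the true rate is 19.3% and the true contrast 8.4 points. Observed contrasts run from 19.8 − 11.5 ≈ 8.2 (unbiased, SD 3, from unrounded rates) down to 16.7 − 9.9 = 6.8 (bias +3, SD 7). Dilution appears again. The missed share depends strongly on the model.

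**6. Unequal error between age groups.** In step 4 the observed rate at a true 10% shifts by −0.8 to +3.6 points. If ART pregnancies were dated without error and the ART share differed by 30 points between age groups (an assumption), the differential shift would be 0.30 × (−0.8 to +3.6) ≈ −0.2 to +1.1 points. One woman in 40 is 2.5 points.

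**7. Transfer date.** If weeks were counted literally from transfer, gestation would be understated by an assumed 17–19 days (14 days plus an embryo age of 3 or 5 days). Under Normal(275, 13), apparent preterm birth would be Φ((259 − 275 + 17)/13) = 53% to Φ((259 − 275 + 19)/13) = 59%, against a true 10.9%.

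**The case against.** The strongest reply is that the protocol does not forbid correction by scan: the LMP sentence sits in a history-taking list, and silence is not a ban. That is fair. But a rule with one named exception is the rule that will be applied, and nothing says when a scan overrides it.

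Second, the effect is small against the study's precision. For 10% versus 25% with 40 per group, the standard error is √(0.10·0.90/40 + 0.25·0.75/40) = 8.3 points. Power with perfect dating is Φ((0.15 − 1.96·√(2·0.175·0.825/40))/0.0833) ≈ 42%. Losing 1 to 4 points of contrast is secondary to that. This stands, and it is why the point is a cheap improvement only.

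Third, neither booking week nor first-scan week is fixed, so monthly scans do not guarantee usable dating for every woman. This also stands.

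A reader might go further and infer that outcomes are in fact misclassified, and unequally, against a sound ART reference. The documents do not support that:
- They give no dating error, cycle data or ART share.
- The dilution in the working comes from equal error in both groups, and step 6 suggests that any differential part between age groups is small.
- The exception covers IVF, while the eligibility and comparison text says ART. Any other ART method therefore falls under the LMP default.
- Transfer dating has no stated conversion, so it is not a clean reference. The literal reading in step 7 shows why the conversion should be written down; nothing shows that it would be applied that way.

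**Conclusion.** The point holds as a risk of misclassification in preterm birth and its early and late classes, which would dilute group contrasts. Under the assumptions in step 2, about 4–22% of true preterm births are missed, about 9–31% of labelled preterm births are false (34% at one corner), and a true 15-point contrast appears as about 11–14 points. The observed rate is about 9–13% (13.6% at that corner) against a true 10%, so it can move either way. The Normal model in step 5 gives larger missed shares, up to 37%, so these ranges illustrate and do not estimate.

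Unequal error between spontaneous and ART pregnancies, and between age groups if ART share differs, is a possibility that the documents do not quantify. Growth restriction is affected only if it is defined by gestational age, and the plan gives no definition. It might also be inferred that the stated 94% power is undermined. That does not follow: the power refers to an overall poor outcome whose components are not stated. No change in sample size is called for.

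**What to change.** In "I. History", item b, state one dating algorithm before data collection:
- **Non-IVF conceptions:** gestational age is confirmed by the earliest scan before a prespecified week. The scan date replaces LMP when the two differ by more than a prespecified number of days, or when LMP is uncertain. LMP alone is used only when no such scan exists.
- **IVF:** state how the transfer date, with embryo age, is converted to menstrual weeks, so that both groups are on the same scale.

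Record the dating method for each woman from enrolment, and add to the statistical analysis a sensitivity analysis excluding women dated by LMP alone. If growth restriction is to be defined by gestational age, say so and use the same dating.

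The cost is a short paragraph and one extra data field, with no added procedure because the scans are already planned. The downside is that late bookers without an early scan remain on LMP.

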**II. Clinical examination: General, abdominal and local examination.**

**General examination:** include blood pressure, pulse, temperature, height and weight to calculate body mass index (BMI) to determine maternal obesity.

- Blood pressure to exclude the hypertensive patients. We will measure blood pressure in each antenatal visit to diagnose the cases which may develop gestational hypertension or preeclampsia after 20 weeks of gestations which will be screened and diagnosed clinically by the obstetricians, according to guidelines (16).

**Abdominal examination:** include obstetric grips.

**Local examination:** when indicated.

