### **Statistical analysis**

Data will be entered and analyzed using IBM-SPSS software (IBM Corp. Released 2017. IBM SPSS Statistics for Windows, Version 25.0. Armonk, NY: IBM Corp.)

Qualitative data will be presented as Number and percent, Quantitative data will be tested for normality using Shapiro-Wilk's test then described as mean and standard deviation for normally distributed data and median and range for non-normally distributed. The appropriate statistical test will be applied according to data type with the following suggested tests: Chi-Square for categorical variable.

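### Does dating IVF pregnancies from embryo transfer, and all others from LMP, mislabel term births as preterm?

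*Combined protocol and SAP*

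**What the plan says.** Under I. History, item b, the general rule is "LMP to detect Gestational age expressed in weeks which calculated from first day of LMP". The next sentence makes the exception for IVF: "For patients who underwent in vitro fertilization, gestational age will be calculated from the date of the embryo transfer". The document gives no number of days to add, does not list embryo age at transfer as an item to record, and gives the monthly ultrasound no stated dating role.

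Under III. Investigations, the maternal outcomes include "preterm birth which is defined as delivery of an infant before 37 weeks of gestation", subdivided into late preterm and "early preterm birth (delivery from 28 to 34 weeks of gestation". These limits are the same for every woman.

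The inclusion criteria admit "natural conception or with using ART", and the Sample size section adds a secondary comparison: "We will also compare between those with spontaneous pregnancy and those with ART". The Statistical analysis section suggests "Chi-Square for categorical variable" and describes no adjustment for mode of conception.

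**The concern.** The two dating sentences are worded in parallel. In the first, the LMP date is day 0 of the count. Read the same way, the second makes the transfer date day 0. Gestational age by LMP already includes about two weeks before fertilisation, and an embryo is some days old when transferred, so the IVF clock would start more than two weeks late while the 34- and 37-week limits stayed put.

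All of that error would fall on the ART side of the spontaneous-versus-ART comparison and could produce an excess of preterm birth with no biological basis. The age comparison would be biased too if IVF were commoner among the older women. That is plausible, since the Introduction itself links late first pregnancy with subfertility. An unadjusted chi-square test would not separate the artefact from a real effect. The rule also mentions IVF only, whereas the eligibility criteria and the planned comparison speak of ART.

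**Working it through.** **The plan's own figure.** The only design calculation is the power statement: 40 against 40, event probabilities 0.20 and 0.60, two-sided Wald test at 0.05. SE of the log odds ratio = √(1/8 + 1/32 + 1/24 + 1/16) = 0.510. Power = Φ(ln 6 / 0.510 − 1.96) = Φ(1.55) = 0.940, which agrees with the stated 94%. Enrolment 80 / (1 − 0.20) = 100 also agrees. Neither figure depends on the dating rule.

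**Day arithmetic if transfer is day 0.** Inputs from the documents: preterm means under 37 weeks, that is under 259 days. Assumptions: 14 days from LMP to fertilisation, embryo age e = 2 to 6 days at transfer.

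- Shortfall = 14 + e, so 16 to 20 days. With e = 0 or 1 it would be 14 or 15.
- Last true gestation recorded as preterm = 258 + shortfall = 274 days (39w1d) to 278 days (39w5d).
- A true 37w0d is recorded as 259 − 16 = 243 days (34w5d) down to 259 − 20 = 239 days (34w1d).
- A true 40w0d is recorded as 280 − 16 = 264 days (37w5d) down to 280 − 20 = 260 days (37w1d).

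**Size on that reading.** Assume true gestation at birth is normal with mean 39.0 and SD 1.5 weeks. Then P(preterm) = Φ((37 − 39)/1.5) = 0.091. With a shift of d days it is Φ((37 + d/7 − 39)/1.5): 0.576 at 16 days, 0.683 at 19, 0.716 at 20.

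The table gives the probability that chi-square at 0.05 rejects when there is no true effect. It comes from exact binomial enumeration with 80 women and a shift of 16 / 19 days. The shares and counts are assumed.

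| Comparison | Scenario | Rejection |
|---|---|---|
| Spontaneous v ART | 4 ART women, all IVF | 0.77 / 0.88 |
| | 4 ART women, half IVF | 0.39 / 0.48 |
| | 8 ART women, all IVF | 0.91 / 0.98 |
| | 8 ART women, half IVF | 0.53 / 0.64 |
| Older v younger | IVF 10% in both | 0.05 / 0.05 |
| | IVF 10% v 5% | 0.07 / 0.07 |
| | IVF 15% v 5% | 0.10 / 0.12 |
| | IVF 50% v 5% | 0.67 / 0.81 |

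With no shift, the same test rejects 0.048 of the time with 4 ART women and 0.051 with 8. The excess is therefore due to dating, not to small cells.

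**Size if the conversion is applied.** Gestational age = days since transfer + 14 + e. The shortfall is 0 days, the limit falls at a true 37w0d for every woman, and every excess in the table disappears.

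**Which reading the text supports.** The sentence says what the calculation starts from, not what value gestational age has on that day. The day-0 reading would also move the rest of antenatal care for IVF women. The protocol's watch for "gestational hypertension or preeclampsia after 20 weeks of gestations" would begin at a true 22w2d to 22w6d (140 + 16 to 140 + 20 days). A woman delivering at a true 40 weeks would be charted as barely past 37. Obstetricians who scan these women every month would meet a discrepancy of over two weeks at each visit.

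**Could it be repaired at analysis?** The shift is a known constant for each woman. The transfer date has to be on file for the rule to be used at all, so gestational age can be recomputed from it. If embryo age were unavailable, using 4 days would be wrong by at most 2 days over the assumed range. On the same normal model the preterm proportion would then lie between Φ((37 − 2/7 − 39)/1.5) = 0.064 and Φ((37 + 2/7 − 39)/1.5) = 0.127, around a true 0.091. The 0.58 to 0.72 of the day-0 reading would not arise.

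**ART without IVF.** A pregnancy with no embryo transfer has no transfer date, so the general LMP rule applies by default, on the same scale as spontaneous pregnancies.

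**The case for a change.** The best case for a change is that the parallel wording does favour the day-0 reading, that the consequence on that reading is severe for a planned comparison, and that one sentence would settle it. Fisher's test would not help: with 8 ART women, all IVF, it still rejects with probability 0.86 to 0.96. Even if staff convert correctly, a reader of the protocol cannot see which scale was used.

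The quotations and the arithmetic stand, and so does the remark that the conversion is unwritten. What does not stand is the step from unwritten to misapplied. The documents do not show that transfer is day 0, and they place dating in the hands of specialists for whom conversion is routine. Nor can it be said that embryo age will go unrecorded: no case form is in the documents, and the protocol says that all obstetrical and clinical data will be recorded.

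Reach is limited as well. Preterm birth is one of about 24 listed outcomes (7 obstetric + 5 maternal + 4 fetal + 8 perinatal, counting amniotic fluid volume and birth weight once each), and none is named primary. The ART comparison has no sample-size basis. For the age comparison, which is the study's aim, modest differences in IVF share move the rejection rate only to 0.07 to 0.12, even on the day-0 reading.

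**Conclusion.** The concern does not call for a change. The protocol leaves out a conversion that its users would ordinarily apply, and with that conversion the bias is zero. The alternative, 16 to 20 days short and 58% to 72% of IVF births labelled preterm, needs the transfer date to be taken as day 0. It also needs 14 days to fertilisation, embryo age of 2 to 6 days, and a normal distribution with mean 39.0 and SD 1.5 weeks. The rejection rates further need ART counts and IVF shares, none of which the documents supply. The day-0 reading is the less natural one. It would show up in routine care, and it could be reversed from dates that must be on file. Sample size and power are untouched. This is missing detail of a kind that analysts and clinicians fill sensibly.

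The conclusion rests on a judgement about how obstetricians at this hospital would read the sentence. It would change only if records showed IVF gestational ages counted from zero at transfer.

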**II. Clinical examination: General, abdominal and local examination.**

**General examination:** include blood pressure, pulse, temperature, height and weight to calculate body mass index (BMI) to determine maternal obesity.

- Blood pressure to exclude the hypertensive patients. We will measure blood pressure in each antenatal visit to diagnose the cases which may develop gestational hypertension or preeclampsia after 20 weeks of gestations which will be screened and diagnosed clinically by the obstetricians, according to guidelines (16).

**Abdominal examination:** include obstetric grips.

**Local examination:** when indicated.

### **III. Investigations:**

- All pregnant women will undergo routine investigations at the first antenatal visit which include: CBC, RH grouping, blood grouping, urine analysis, fasting and postprandial blood glucose.

-All pregnant women will be screened for gestational diabetes mellitus (GDM) with a 50-g oral glucose challenge test between 24 and 28 weeks of gestation. Women with abnormal glucose challenge test (140 mg/dL) will undergo a 3-hour oral glucose tolerance test with a 100-g oral glucose load. The diagnosis of GDM will be made when levels of blood glucose are fasting plasma glucose above 95 mg/dL, 1 hour postprandial above 130-140 mg/dL, and 2 hours postprandial above 120mg/dL according to The American College of Obstetricians and Gynecologists (ACOG) recommendations (17).

- All pregnant women will undergo a monthly ultrasound examination until delivery.

- All obstetrical and clinical data will be recorded and collected in an appropriate database.

-Obstetric outcomes will be recorded regarding pregnancy induced hypertension, gestational diabetes mellitus (GDM), anemia, antepartum hemorrhage, oligohydraminos or polyhydraminos, obtetretic shock and intrapartum hemorrhage.

-Maternal outcomes will be recorded regarding mode of delivery “cesarean or vaginal delivery”, premature rupture of membranes, preterm birth which is defined as delivery of an infant before 37 weeks of gestation and will be classified into late preterm (from 34 to less than 37 weeks of gestation) and early preterm birth (delivery from 28 to 34 weeks of gestation), obstructed labor and prolonged labor.

-Fetal outcomes will be recorded regarding congenital malformations, intrauterine growth restriction, intrauterine fetal death and stillbirth.

- Perinatal outcomes will be recorded regarding birth weight which will be classified into low birth weight (less than 2500 g), very low birth weight (less than 1500 g) and macrosomia (more than 4000 g), birth asphyxia, meconium aspiration syndrome, NICU admission, neonatal hypoglycemia, Hyperbilirubinemia, 5-Min Apgar score less than 7 and neonatal death.

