Risk of spontaneous abortion between 6 to 14 weeks of pregnancy increased with increasing maternal age (11). Late pregnancy outcomes including Gestational DM and preeclampsia which increasing up to 10% in women more 40 years of age and higher up to 35% in women more than 50 years of age which may cause intra uterine growth retardation and stillbirth (12).

Advanced maternal age is also linked to a higher prevalence of placenta praevia and placental abruption, both of which cause bleeding in late pregnancy (after about 20 weeks) especially in multipara (13). Women more than 40 years of age showed an eight-fold increased risk of amniotic fluid embolism due to increased incidence of caesarian section and a three-fold increased risk of obstetric shock compared with women age 25–29 years (14).

According to the royal college of obstetricians and gynecologists, the optimum period for child bearing is between 20 and 35 years of age to decrease maternal and neonatal complications (15).

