### **Aim of work**

This study to evaluate the effect of advanced maternal age on the outcomes of pregnancy which include: maternal, obstetric, fetal and perinatal outcomes.

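### The early and late preterm classes overlap at 34 weeks and leave deliveries under 28 weeks unclassified; secondarily, early pregnancy loss has no named category

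*Combined protocol and SAP*

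**What the plan says.** Everything here is in the combined protocol and SAP.

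- **Preterm birth.** Section III, Investigations, lists under maternal outcomes "preterm birth which is defined as delivery of an infant before 37 weeks of gestation", with no lower limit. It then divides these births into "late preterm (from 34 to less than 37 weeks of gestation) and early preterm birth (delivery from 28 to 34 weeks of gestation".
- **Gestational age.** Section I, History, has "Gestational age expressed in weeks which calculated from first day of LMP", or from the embryo transfer date after in vitro fertilization.
- **Fetal outcomes.** "Fetal outcomes will be recorded regarding congenital malformations, intrauterine growth restriction, intrauterine fetal death and stillbirth". No gestational limits are attached. None of the four outcome lists names miscarriage, ectopic pregnancy or termination.
- **Rationale and aim.** The Introduction names ectopic pregnancy as an early outcome linked to maternal age and adds "Risk of spontaneous abortion between 6 to 14 weeks of pregnancy increased with increasing maternal age". The Aim of work is "to evaluate the effect of advanced maternal age on the outcomes of pregnancy which include: maternal, obstetric, fetal and perinatal outcomes".
- **Entry.** The Inclusion criteria take women "who seeking for routine antenatal care to the university hospital" and set no gestational age at entry.
- **Dropout and analysis.** The Sample size section allows 20% dropout (20 of 100 women) without defining it. The Statistical analysis section has no rule for pregnancies that end early.

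**The concern.** A classification should give each event exactly one class. This one fails at both ends of its early class: it starts at 28 weeks while the parent definition has no floor, and it shares 34 weeks with the late class. Two people following the text faithfully could report different early and late counts from the same records, and the two counts could sum to more or less than the number of preterm births.

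The second gap is an omission. The Introduction gives early loss as a reason to study maternal age, yet a woman who enrols early and miscarries has no named outcome. Unless her loss is recorded as intrauterine fetal death, the plan does not say where it goes, and nothing rules out its being treated as dropout. An age-related event could then be missing from the fetal results, and dropout could differ by age group for a reason the report does not show.

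**Working it through.** **1. Preterm classes against the definition**

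| Gestation at delivery | Preterm? | Early (28 to 34) | Late (34 to <37) |
|---|---|---|---|
| under 28 | yes | no | no |
| 28 to before 34 | yes | yes | no |
| 34 | yes | yes | yes |
| after 34, before 37 | yes | no | yes |

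The same sentence excludes the upper limit at 37 but not at 34, so a strict limit at 34 cannot be taken for granted. If gestational age is kept in whole weeks (an assumption), the overlap is week 34, one of the three late-preterm weeks 34, 35 and 36. If days are kept, it may shrink to a single day.

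Illustration with assumed counts, since the documents give no preterm rate: 1 birth under 28 weeks, 3 at 28–33, 2 at 34 and 4 at 35–36, total 10.
- Early: 3, or 3 + 2 = 5.
- Late: 4, or 4 + 2 = 6.
- Read literally, the classes sum to 5 + 6 = 11, with 1 birth in neither.

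**2. The plan's own power figure**

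Inputs from the Sample size section: 20% against 60% poor outcome, 40 per group, two-sided Wald test, alpha 0.05.
- OR = (0.6/0.4)/(0.2/0.8) = 6.
- SE of log OR = sqrt(1/(40×0.2×0.8) + 1/(40×0.6×0.4)) = 0.510.
- Power = Φ(ln 6/0.510 − 1.96) = 0.940, the stated 94%.
- Enrolment = 80/(1 − 0.20) = 100, as stated.

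**3. What early loss could do to the main comparison**

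The documents give no loss rate. Assume 2 to 10 losses among 50 older women and 1 to 4 among 50 young women. They also do not say whether the 20% and 60% include early losses, so both readings are shown.

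*Reading A: the rates exclude losses, and losses are added as poor outcomes.* Risk = L + (1 − L)p, where L is the proportion lost.
- 6 vs 2: older 0.12 + 0.88×0.60 = 0.648; young 0.04 + 0.96×0.20 = 0.232; risk difference (RD) 0.416.
- Lowest RD, 2 vs 4: 0.616 − 0.264 = 0.352. Highest, 10 vs 1: 0.680 − 0.216 = 0.464.
- Power for 6 vs 2 at these risks (OR 6.09): SE 0.477 and about 97% with 44 per group (the other 12 dropouts split evenly); SE 0.447 and about 98% with 50 per group (no dropout).
- If the 8 losses are instead excluded with 60% and 20% unchanged, 38 older and 42 young women remain: SE 0.508, power 94%.

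*Reading B: the rates include losses, and losses are dropped.* Risk = (poor outcomes − losses)/(50 − losses), from 30 older and 10 young poor outcomes.
- 10 vs 1: older 20/40 = 0.500; young 9/49 = 0.184; RD 0.316. With 20 dropouts in all, the other 9 split evenly, the groups are 35.5 and 44.5: OR 4.44, SE 0.512, power Φ(1.492/0.512 − 1.96), about 83%.
- 2 vs 4: older 28/48 = 0.583; young 6/46 = 0.130; RD 0.453.

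The RD can therefore fall below or rise above the planned 0.40 under either reading.

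**The case against.** On the preterm classes, the upper limit of the early class may be loose wording for less than 34 weeks, and days can be derived from the LMP or transfer date. Both are fair and limit the practical effect, but the text does not state the strict limit, and neither point gives a delivery under 28 weeks a class. If 28 weeks was meant as the floor for a birth, the preterm definition omits it. A reader might infer that the preterm outcome as a whole is unusable. It is not: only births at 34 or under 28 weeks are ambiguous, and the overall preterm count stands.

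On early loss, the case against is stronger. Intrauterine fetal death has no lower gestational limit and could take in some losses. The plan also says "All obstetrical and clinical data will be recorded and collected in an appropriate database", and ultrasound is monthly. If most women enrol after 14 weeks, few early losses would occur. A reader might infer that losses will be coded as dropout and the main comparison biased. The documents do not say so: the 20% is only a planning allowance. What remains is that recording data does not assign a category, and an undefined fetal-death item lets the same loss be coded in different ways.

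A reader might also conclude that early loss affects only the visibility of an outcome and leaves power alone. That would require the 20% and 60% to exclude early losses, which the plan does not state.

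**Conclusion.** The preterm classification is wrong as written and should be corrected; this follows from the text with no assumption. Its size depends on how many births fall at 34 or under 28 weeks, and it is zero if there are none.

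The early-loss point is secondary and less certain. The omission from all four lists is a fact, while the route into dropout is only a possibility. Its effect on the main comparison is unknown in size and direction. Under the assumed loss numbers, the RD runs from 0.352 to 0.464 if losses are added as poor outcomes. It is about 0.32, with power about 83%, in the 10 vs 1 case if the planned rates already include losses and those losses are dropped. These figures illustrate the uncertainty and are not estimates.

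**What to change.** **Preterm classes (no cost).** Use classes that do not overlap and cover the definition, for example under 28, 28 to under 34, and 34 to under 37 weeks. If 28 weeks is the intended floor for a birth, put it in the preterm definition too, and make the early class end before 34.

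**Early pregnancy loss (a small addition to the record form).**
- Record miscarriage, ectopic pregnancy and termination separately, with gestational age at entry and at loss. The dating method is already in the History section.
- State one gestational boundary separating early loss from intrauterine fetal death, stillbirth and preterm birth, so that each event is counted once.
- Report number and percent by age group among all enrolled women, separately from loss to follow-up. This is already the planned presentation for qualitative data.
- State whether the overall poor outcome in the Sample size section includes early loss.

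The downside is an imprecise comparison of few events, which should be presented as descriptive.
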